12.3.2 Attribution Definitions

The relationship, or attribution, of an adverse event to the study therapy regimen or study procedure(s) will initially be determined by the site investigator and recorded on the appropriate *AE/SAE eCRF*. Final determination of attribution for safety reporting will be determined by DAIT/NIAID. The relationship of an adverse event to study therapy regimen or procedures will be determined using the descriptors and definitions provided in Table 14.

For additional information and a printable version of the NCI-CTCAE manual, consult the NCI-CTCAE web site: <http://ctep.cancer.gov/reporting/ctc.html>.

Table 14: Attribution of Adverse Events

Code	Descriptor	Relationship (to primary investigational product and/or other concurrent mandated study therapy or study procedure)
UNRELATED CATEGORY		
1	Unrelated	The adverse event is clearly not related: there is insufficient evidence to suggest a causal relationship.
RELATED CATEGORIES		
2	Possible	The adverse event has a reasonable possibility to be related; there is evidence to suggest a causal relationship.
3	Definite	The adverse event is clearly related.

12.4 Collection and Recording of Adverse Events

12.4.1 Collection Period

Adverse events will be collected from the time of enrollment until a subject completes study participation or until 30 days after he/she prematurely withdraws (without withdrawing consent) or is withdrawn from the study.

12.4.2 Collecting Adverse Events

Adverse events (including SAEs) may be discovered through any of these methods:

- Observing the subject.
- Interviewing the subject [e.g., using a checklist, structured questioning, diary, etc.].
- Receiving an unsolicited complaint from the subject.
- In addition, an abnormal value or result from a clinical or laboratory evaluation can also indicate an adverse event, as defined in Section 12.3, Grading and Attribution of Adverse Events.

12.4.3 Recording Adverse Events

Throughout the study, the investigator will record adverse events and serious adverse events as described previously (Section 12.2, Definitions) on the appropriate AE/SAE eCRF regardless of the relationship to study therapy regimen or study procedure.

Once recorded, an AE/SAE will be followed until it resolves with or without sequelae, or until the end of study participation, or until 30 days after the subject prematurely withdraws (without withdrawing consent)/or is withdrawn from the study, whichever occurs first.

12.5 Reporting of Serious Adverse Events and Adverse Events

12.5.1 Reporting of Serious Adverse Events to Sponsor

This section describes the responsibilities of the site investigator to report serious adverse events to the sponsor via the SAE eCRF. Timely reporting of adverse events is required by 21 CFR and ICH E6 guidelines.

Site investigators will report all serious adverse events (see Section 12.2.3, Serious Adverse Event), regardless of relationship or expectedness within 24 hours of discovering the event.

For serious adverse events, all requested information on the AE/SAE eCRF will be provided. However, unavailable details of the event will not delay submission of the known information. As additional details become available, the AE/SAE eCRF will be updated and submitted.

12.5.2 Reporting to Health Authority

After an adverse event requiring 24 hour reporting (per Section 12.5.1, Reporting of Serious Adverse Events to Sponsor) is submitted by the site investigator and assessed by DAIT/NIAID, there are two options for DAIT/NIAID to report the adverse event to the appropriate health authorities:

12.5.2.1 Annual Reporting

DAIT/NIAID will include in the annual study report to health authorities all adverse events classified as:

- Serious, expected, suspected adverse reactions (see Section 12.2.1.1, *Suspected Adverse Reaction*, and Section 12.2.2, *Unexpected Adverse Event*).
- Serious and not a suspected adverse reaction (see Section 12.2.2, *Suspected Adverse Reaction*).
- Pregnancies.

Note that all adverse events (not just those requiring 24-hour reporting) will be reported in the Annual IND Report.

12.5.2.2 Expedited Safety Reporting

This option, with 2 possible categories, applies if the adverse event is classified as one of the following:

Category 1: Serious and unexpected suspected adverse reaction [SUSAR] (see Section 12.2.1.1, *Suspected Adverse Reaction* and Section 12.2, *Unexpected Adverse Event* and 21 CFR 312.32(c)(1)i).

The sponsor shall report any suspected adverse reaction that is both serious and unexpected. The sponsor shall report an adverse event as a suspected adverse reaction only if there is evidence to suggest a causal relationship between the study drug and the adverse event, such as:

1. A single occurrence of an event that is uncommon and known to be strongly associated with drug exposure (e.g., angioedema, hepatic injury, or Stevens-Johnson Syndrome);
2. One or more occurrences of an event that is not commonly associated with drug exposure, but is otherwise uncommon in the population exposed to the drug (e.g., tendon rupture);
3. An aggregate analysis of specific events observed in a clinical trial (such as known consequences of the underlying disease or condition under investigation or other events that commonly occur in the study population independent of drug therapy) that indicates those events occur more frequently in the drug treatment group than in a concurrent or historical control group.

Category 2: Any findings from studies that suggests a significant human risk

The sponsor shall report any findings from other epidemiological studies, analyses of adverse events within the current study or pooled analysis across clinical studies or animal or *in vitro* testing (e.g. mutagenicity, teratogenicity, carcinogenicity) that suggest a significant risk in humans exposed to the drug that would result in a safety-related change in the protocol, informed consent, investigator brochure or package insert or other aspects of the overall conduct of the study.

DAIT/NIAID shall notify the FDA and all participating investigators of expedited Safety Reports within 15 calendar days; unexpected fatal or immediately life-threatening suspected adverse reaction(s) shall be reported as soon as possible or within 7 calendar days.

12.5.3 Reporting of Adverse Events to IRBs/IECs

All investigators shall report adverse events, including expedited reports, in a timely fashion to their respective IRBs/IECs in accordance with applicable regulations and guidelines. All Safety Reports to the FDA shall be distributed by DAIT/NIAID or designee to all participating institutions for site IRB/IEC submission.

12.6 Pregnancy Reporting

The investigator shall be informed immediately of any pregnancy in a study subject or a partner of a study subject. A pregnant subject shall be instructed to stop taking study medication. The investigator shall counsel the subject and discuss the risks of continuing with the pregnancy and the possible effects on the fetus. Monitoring of the pregnant subject shall continue until the conclusion of the pregnancy.

The investigator shall report to the SACCC all pregnancies within 1 business day of becoming aware of the event using the Pregnancy eCRF. All pregnancies identified during the study shall be followed to conclusion and the outcome of each must be reported. The Pregnancy eCRF shall be updated and submitted to SACCC when details about the outcome are available. When possible, similar information shall be obtained for a pregnancy occurring in a partner of a study subject.

Information requested about the delivery shall include:

- Gestational age at delivery
- Birth weight, length, and head circumference
- Gender
- Appearance, pulse, grimace, activity, and respiration (APGAR) score at 1 minute, 5 minutes, and 24 hours after birth, if available
- Any abnormalities.

All pregnancy complications that result in a congenital abnormality, birth defect, miscarriage, and medically indicated abortion - an SAE shall be submitted to the SACCC using the SAE reporting procedures described above.

12.7 Reporting of Other Safety Information

An investigator shall promptly notify the site IRB as well as the SACCC when an “unanticipated problem involving risks to subjects or others” is identified, which is not otherwise reportable as an adverse event.

12.8 Review of Safety Information

12.8.1 Medical Monitor Review

The *DAIT/NIAID* Medical Monitor shall receive monthly reports from the SACCC compiling new and accumulating information on AEs, SAEs, and pregnancies recorded by the study site(s) on appropriate eCRFs.

In addition, the Medical Monitor shall review and make decisions on the disposition of the SAE and pregnancy reports received by the SACCC (See Sections 12.5.1, *Reporting of Serious Adverse Events to Sponsor*, and 12.6, *Pregnancy Reporting*).

12.8.2 DSMB Review

12.8.2.1 Planned DSMB Reviews

The Data and Safety Monitoring Board (DSMB) shall review safety data at least yearly during planned DSMB Data Review Meetings. Data for the planned safety reviews will include, at a minimum, a listing of all reported AEs and SAEs.

The DSMB will be informed of an Expedited Safety Report in a timely manner.

12.8.2.2 *Ad hoc* DSMB Reviews

In addition to the pre-scheduled data reviews and planned safety monitoring, the DSMB may be called upon for *ad hoc* reviews. The DSMB will review any event that potentially impacts safety at the request of the study principal investigator or DAIT/NIAID. In addition, satisfaction of any of the following **stopping rules** in study subjects at any time of follow-up in the treatment arms will trigger an *ad hoc* DSMB Safety Review:

- Any occurrence of confirmed PML.
- Incidence of death of 30% or more subjects.
- Incidence of at least mild acute rejection of 35% or more.
- Incidence of humoral rejection of 25% or more.
- Incidence of primary graft dysfunction of 50% or more.
- Incidence of PTLD of 5% or more.
- Incidence of infections of any type requiring hospitalization of 40% or more.

The thresholds for stopping rules involving subject-level incidence rates have been formulated based on an analysis of adverse events in the CTOTC-03 (NCT00891865) observational study of subjects who are similar to those in the control arm of this study. They will be evaluated routinely by the SACCC with the occurrence of any of the triggering events throughout follow-up of subjects within either randomized treatment arm. They will be implemented by comparing the exact lower 95% confidence limit on the currently observed subject-level incidence rate to the threshold rate described for that event in the stopping rule. If the lower confidence limit is greater than the threshold, the stopping rule will be considered to have been met and the Medical Monitor, DSMB and study PI will be notified.

Following are tables illustrating, for each stopping rule, the minimum numbers of subjects with the respective event that would meet the stopping rule for selected numbers of subjects within either randomized treatment arm:

Table 15: Minimum Numbers of Subjects with the Event in Either Randomized Treatment Arm that meet the Stopping Rule for Death with a Threshold of Concern of 30%

Number of Subjects with Event	Number of Randomized Subjects	Cumulative Incidence Rate	Lower 95% Confidence Limit
4	4	100.00	47.29
5	6	83.33	41.82
6	8	75.00	40.03
6	10	60.00	30.35
7	12	58.33	31.52
8	14	57.14	32.50
9	16	56.25	33.34
10	18	55.56	34.06
10	20	50.00	30.20
11	22	50.00	31.13

Table 16: Minimum Numbers of Subjects with the Event in Either Randomized Treatment Arm that meet the Stopping Rule for Mild Acute Rejection with a Threshold of Concern of 35%

Number of Subjects with Event	Number of Randomized Subjects	Cumulative Incidence Rate	Lower 95% Confidence Limit
4	4	100.00	47.29
5	6	83.33	41.82
6	8	75.00	40.03
7	10	70.00	39.34
8	12	66.67	39.09
9	14	64.29	39.04
10	16	62.50	39.10
11	18	61.11	39.22
11	20	55.00	34.69
12	22	54.55	35.25

Table 17: Minimum Numbers of Subjects with the Event in Either Randomized Treatment Arm that meet the Stopping Rule for Humoral Rejection with a Threshold of Concern of 25%

Number of Subjects with Event	Number of Randomized Subjects	Cumulative Incidence Rate	Lower 95% Confidence Limit
4	4	100.00	47.29
4	6	66.67	27.13
5	8	62.50	28.92
6	10	60.00	30.35
7	12	58.33	31.52
7	14	50.00	26.36
8	16	50.00	27.86
9	18	50.00	29.12
9	20	45.00	25.87
10	22	45.45	27.13

Table 18: Minimum Numbers of Subjects with the Event in Either Randomized Treatment Arm that meet the Stopping Rule for Primary Graft Dysfunction with a Threshold of Concern of 50%

Number of Subjects with Event	Number of Randomized Subjects	Cumulative Incidence Rate	Lower 95% Confidence Limit
5	4	100.00	54.93
6	6	100.00	60.70
7	8	87.50	52.93
9	10	90.00	60.58
10	12	83.33	56.19
11	14	78.57	53.43
12	16	75.00	51.56
13	18	72.22	50.22
15	20	75.00	54.44
16	22	72.73	53.15

Table 19: Minimum Numbers of Subjects with the Event in Either Randomized Treatment Arm that meet the Stopping Rule for PTLD with a Threshold of Concern of 5%

Number of Subjects with Event	Number of Randomized Subjects	Cumulative Incidence Rate	Lower 95% Confidence Limit
2	4	50.00	9.76
2	6	33.33	6.28
3	8	37.50	11.11
3	10	30.00	8.73
3	12	25.00	7.19
3	14	21.43	6.11
3	16	18.75	5.31
4	18	22.22	7.97
4	20	20.00	7.14
4	22	18.18	6.46

Table 20: Minimum Numbers of Subjects with the Event in Either Randomized Treatment Arm that meet the Stopping Rule for Infection Requiring Hospitalization with a Threshold of Concern of 40%

Number of Subjects with Event	Number of Randomized Subjects	Cumulative Incidence Rate	Lower 95% Confidence Limit
4	4	100.00	47.29
5	6	83.33	41.82
6	8	75.00	40.03
8	10	80.00	49.31
9	12	75.00	47.27
10	14	71.43	46.00
11	16	68.75	45.17
12	18	66.67	44.60
13	20	65.00	44.20
14	22	63.64	43.91

After review of the data, the DSMB will make recommendations regarding study conduct and/or continuation.

12.8.2.2.1 Temporary Suspension of *enrollment and drug dosing* for *ad hoc* DSMB Safety Review

A temporary halt in enrollment, randomization and administration of rituximab/rituximab placebo will be implemented if an ad hoc DSMB safety review is required. In the event a study participant has already received the first dose of rituximab/rituximab placebo, every attempt will be made to expedite review such that a prompt decision can be made regarding the appropriate management for these subjects.

13. Statistical Considerations and Analytical Plan

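### Two rows of the stopping-rule tables contradict the written rule: Table 16 lists 11 of 20 although its limit is below 35%, and Table 18 lists 5 events in 4 subjects

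*Protocol*

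**What the plan says.** Section 12.8.2.2 of the protocol (Ad hoc DSMB Reviews) lists the thresholds, among them "Incidence of at least mild acute rejection of 35% or more" and 50% for primary graft dysfunction. It says the rules are applied by "comparing the exact lower 95% confidence limit on the currently observed subject-level incidence rate to the threshold rate" set for that event. The criterion is strict: "If the lower confidence limit is greater than the threshold, the stopping rule will be considered to have been met". The tables that follow are said to illustrate, for selected arm sizes, "the minimum numbers of subjects with the respective event that would meet the stopping rule".

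- Table 16, headed in part "Stopping Rule for Mild Acute Rejection with a Threshold of Concern of 35" (per cent), row for 20 randomized subjects: "11 20 55.00 34.69", that is, 11 events, 20 subjects, 55.00%, lower limit 34.69%.
- Table 18, headed in part "Stopping Rule for Primary Graft Dysfunction with a Threshold of Concern of 50" (per cent), first row: 5 events, 4 subjects, 100.00%, lower limit 54.93%.

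Section 12.8.2.2.1 attaches a temporary stop in enrollment, randomization and infusions to any required ad hoc review. The SAP repeats the percentage thresholds in its synopsis, and its section 9 refers back to the protocol's stopping rules. It gives neither the confidence-limit criterion nor the tables.

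**The concern.** Each table row should satisfy the rule it illustrates. The Table 16 row fails on its face, since 34.69 is not greater than 35. The Table 18 row cannot occur, since events are counted per subject and five of four subjects cannot have one.

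What is at stake is a clear trigger for a safety review that carries a temporary halt. With 50 subjects randomized 1:1, about 25 per arm, each arm should pass through n = 20. If an arm then has 11 subjects with acute rejection, the table says the rule is met and the text says it is not.

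A related gap is that the text gives a lower 95% limit without saying whether it is one-sided or two-sided. The tables are the only place where a reader can find out.

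**Working it through.** **Inputs.** The criterion, the thresholds and all 60 rows come from protocol section 12.8.2.2, Tables 15 to 20.

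**Formula.** The exact (Clopper-Pearson) one-sided 95% lower limit L for x events in n subjects solves P(X ≥ x | n, L) = 0.05. Equivalently, L is the 0.05 quantile of a Beta(x, n − x + 1) distribution. When x = n this reduces to L = 0.05^(1/n). It follows that L exceeds a threshold p0 exactly when P(X ≥ x | n, p0) < 0.05.

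**1. Which limit do the tables use?** Tables 15, 16, 17 and 20 open with "4 4 100.00 47.29".
- One-sided: 0.05^(1/4) = 47.29%, as printed.
- Two-sided: 0.025^(1/4) = 39.76%, not as printed.

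The tables use the one-sided limit.

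**2. All 60 rows.** Two separate checks were made.
- Printed limits: 59 of 60 reproduce to two decimals. The exception is Table 18, row 1.
- Minimum counts under the written rule: 58 of 60 rows are correct. The exceptions are Table 18, row 1, and Table 16, n = 20.

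**3. Table 16, n = 20, threshold 35%.**
- 11/20: L = 34.69%, so the printed limit is reproduced. It falls 35 − 34.69 = 0.31 percentage points short. P(X ≥ 11 | 20, 0.35) = 0.0532, above 0.05, so the rule is not met.
- 12/20 = 60.00%: L = 39.36%. P(X ≥ 12 | 20, 0.35) = 0.0196, below 0.05, so the rule is met.
- With a two-sided limit the cut-off for the tail is 0.025. Since 0.0196 < 0.025 < 0.0532, the minimum is again 12 (the two-sided limit for 11/20 is 31.53%).

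The limit in this row is right, but the count is not one that meets the rule.

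**4. Table 18, first row, threshold 50%.**
- 5/5: rate 100.00%, L = 0.05^(1/5) = 54.93%. These are the printed rate and limit, so only the denominator of 4 is out of line.
- 4/4: L = 47.29%, below 50%; P(4 of 4 | 0.50) = 0.0625. Fewer events give a lower limit, so no count at n = 4 meets the rule.

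**5. How much does sidedness matter?** This step compares the one-sided and two-sided minimum counts under the written rule, row by row. The numbers of rows that change in Tables 15 to 20 are 6 + 4 + 6 + 5 + 3 + 3 = 27 of 60. For example, at n = 20 the death count moves from 10 to 11 and the humoral rejection count from 9 to 10. In Table 20 at n = 4 the rule could no longer be met.

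**The case against.** The strongest reply is that the tables are not the operative rule. They are introduced as illustrations for selected arm sizes. The coordinating center evaluates the rules as triggering events occur by computing the limit, and it notifies the Medical Monitor, the DSMB and the study PI if a rule is met. Nobody is told to read a count off a table. This stands. A reader might infer that the trial would be halted at 11 of 20, but the documents do not describe that procedure. The Table 16 slip also points toward an earlier review rather than a missed one. The consequence would be a review with a temporary pause, and the DSMB can be asked to review a safety concern in any case.

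Two attempts to rescue 11 of 20 fail.
- The bullet for acute rejection could be read as an observed rate, and 55% is above 35%. The minimum would then be 7 of 20 (35%), not 11, and the section says the confidence limit is what is compared.
- Rounding 34.69 to 35 and accepting equality would admit the row. The same convention would admit 3/4 (24.86%) and 6/12 (24.53%) in Table 17, 2/8 (4.64%) and 3/18 (4.70%) in Table 19, and 13/22 (39.52%) in Table 20. In each case the table prints one event more.

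For Table 18, a misprint or a PDF reading error in the denominator cell is possible. That does not save an n = 4 row, because no count there meets the rule. The row also has essentially no decision effect: 5 of 4 can never be observed, and the written rule triggers nothing at n = 4 either.

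A reader might also infer that the tables are unreliable as a whole. The recalculation shows otherwise.

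**Conclusion.** The point holds as a limited correction. Two of the 60 rows are inconsistent with the written rule: one lists a count that does not meet it, and one is impossible as printed. The other 58 are right. The only conflict that could affect a decision is one event at one arm size (11 against 12 acute-rejection subjects among 20), with a limit 0.31 percentage points below the threshold.

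The missing word one-sided is a point of clarity, not a further error. The valid rows already identify the limit, but a two-sided reading would change 27 of 60 minimum counts, so the text should not leave it to inference.

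The verdict assumes that the written criterion, with its strict inequality, is the governing rule and that exact means Clopper-Pearson. The match of 59 of 60 printed limits supports the second assumption.

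**What to change.** Reconcile the tables with the text of section 12.8.2.2. As the rule now stands:

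- Table 16, n = 20: 12 events, 60.00%, lower limit 39.36%.
- Table 18, first row: either mark n = 4 as unable to meet the rule, or replace the row with n = 5 (5 events, 100.00%, lower limit 54.93%).
- Text: add the word one-sided before the reference to the 95% limit, to match the tables.

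If the sponsor did intend 11 of 20 to trigger a review, the text is what needs to change, and the two must still agree. The cost is two table rows and one word, carried in the next protocol amendment. With the rule kept as written, no threshold, sample size or analysis changes.

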13.1 Overview

In this randomized controlled clinical trial, we will compare primary pediatric lung transplant recipients given rituximab induction therapy plus standard immunosuppression to subjects given a placebo induction therapy plus standard immunosuppression and assess whether rituximab induction therapy improves outcomes in this population.

13.2 Endpoints and Safety Outcomes

The primary endpoint will be the earliest time to any of the following events during the follow up period: Chronic Allograft Dysfunction, listing for retransplantation, and death.

The following secondary clinical endpoints will be assessed during the post-transplant follow-up period, which will be a minimum of 12 months:

- incidence of chronic allograft dysfunction, listing for retransplant or death,
- incidence of Primary Graft Dysfunction,
- incidence of Grade A Acute Rejection,
- incidence of Antibody Mediated Rejection,
- incidence of TVT,
- percentage of participants identified to participate completing the TVI,
- and magnitude of change in standard deviation of tacrolimus levels following intervention.

The following secondary clinical post-transplant safety outcomes will be assessed: incidence and severity of infection episodes, and serious adverse events related to rituximab.

The following mechanistic endpoints will be assessed: incidence and kinetics of DSA and auto-antibodies, specifically Collagen V (ColV) and κ -alpha-1 tubulin ($\kappa\alpha 1T$); frequency, kinetics, phenotype and function of peripheral B cells; frequency, kinetics and cytokine profiles of allo- and auto reactive T cells; the incidence and quantity of B cells and B cell proximity to other cells in the graft tissue.

13.3 Measures to Minimize Bias

Study treatments will be randomly assigned to eligible subjects and the treatment assignment of each subject will be double-blinded. In addition, the central laboratories that perform the mechanistic assays will be blinded to both the treatment assignment and clinical status of all study subjects.

